 - Age at baseline
 - Age groups
 - Gender at birth
 - Marital status (married, unmarried)
 - Medical plan type
 - ✓ The type of healthcare plan each patient is enrolled in at baseline will be determined, including National/Public insurance, Private insurance, Employer benefits, and Other
- **Clinical characteristics**
 - Initial Diagnosis of Rheumatoid Arthritis (RA)
 - ✓ Year of initial diagnose
 - Initiation of Adalimumab
 - ✓ First time administration (DD/MM/YYYY)
 - ✓ Dosage of first injection (in mg)
 - Disease status of RA
 - ✓ Moderate (defined as Disease Activity Score in 28 Joints (DAS28) between 3.2 and 5.1)
 - ✓ Severe (DAS28>5.1)
 - Erythrocyte sedimentation rate (ESR) (in mm/hour)
 - C reactive protein (CRP) (in mg/L)
 - Disease Activity Score in 28 joints (DAS28)

To calculate the DAS28, the physician or specialist nurse will:

1. Count the number of swollen joints (out of the 28)
2. Count the number of tender joints (out of the 28)
3. Take blood to measure the erythrocyte sedimentation rate (ESR) or C reactive protein (CRP); the latest measurement in the medical records may also be used if a blood draw is not standard for that visit

4. Ask the patient to make a 'global assessment of health' which will be indicated by marking a 10 cm line between very good and very bad

The physician or specialist nurse will then mark each component score on the CRF and the DAS28 score if calculated (an online scoring calculator for the DAS28 can be found at <http://www.das-score.nl/das28/DAScalculators/dascalculators.html>).

The DAS28 will be scored using the following formula:

$$\text{DAS28} = 0.56 * \text{sqrt}(\text{tender28}) + 0.28 * \text{sqrt}(\text{swollen28}) + 0.70 * \ln(\text{ESR or CRP}) + 0.014 * (\text{Global assessment of Health})$$

DAS28 scores will be interpreted using the following categorization:

- ✓ Remission: DAS28 \leq 2.6
- ✓ Low Disease Activity: $2.6 < \text{DAS28} \leq 3.2$
- ✓ Moderate Disease Activity: $3.2 < \text{DAS28} \leq 5.1$
- ✓ High Disease Activity: DAS28 > 5.1

– comorbidities

- ✓ Myocardial infarction
- ✓ Congestive heart failure
- ✓ Peripheral vascular disease
- ✓ Cerebrovascular disease
- ✓ Dementia
- ✓ Chronic pulmonary disease
- ✓ Connective tissue disease
- ✓ Ulcer disease
- ✓ Mild liver disease
- ✓ Diabetes
- ✓ Hemiplegia
- ✓ Moderate or severe renal disease
- ✓ Diabetes with end-organ damage
- ✓ Any tumor
- ✓ Leukemia
- ✓ Lymphoma
- ✓ Moderate or severe liver disease
- ✓ Metastatic solid tumor
- ✓ AIDS

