3.5.3 Other Co-Variates/Control Variables

Baseline demographics and clinical characteristics will be used in statistical analysis models.

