5.5 Analysis Plan for Exploratory Objectives

- Excel Table 7 describes the change in 4 patient satisfaction questions at weeks 12 and 24 after the initiation of adalimumab, in those patients continuing on adalimumab (observed population). These changes will be summarized as number and percentage of each response and compared with Wilcoxon signed rank test shown by p-value1. Satisfaction will also be dichotomized and analyzed over time with Cochran-Armitage test for trends shown by p-value2 in the table.
- Excel Table 8 summarizes the patients' global impression of change in RA at weeks 12 and 24 after the initiation of adalimumab, in those patients continuing on adalimumab (as observed population). Each response (very much better, much better, a little better, no change, a little worse, much worse, and very much worse) will be summarized as number and percentage.
- Descriptive statistics will be presented for post-index overall RA related direct healthcare resource utilization (Excel Table 9)
 - Consultations/visits to healthcare professionals for treatment of RA (number of patients with ≥ 1 visit; categorized by the treatment department listed in 3.5.4)
 - Procedures received when visiting the healthcare professional(s) for treatment of RA (number of patients with ≥ 1 procedure; categories listed in 3.5.4)
 - surgeries received when visiting the healthcare professional(s) for treatment of RA (number of patients with ≥ 1 surgery; categories listed in 3.5.4)
 - Hospitalizations in relation to RA (number of patients with ≥ 1 admission)
 - Length of stay in days (mean, SD, median)
 - Concomitant medications taken for RA (number of patients with ≥ 1 medication; categories listed in 3.5.4))
- Associations between disease severity (measured by DAS28) and PROs (HAQ DI score, SF-36 domain scales, EQ-5D-3L index, WPAI outcomes) will be analyzed using the bivariate linear regression model (Excel Table 10.1). Separate models will be estimated to identify the association between DAS28 and each of the PROs.
- Additionally, in Excel Table 10.2, separate bivariate liner regression models will be estimated to identify the association between change in DAS28 and change in each of the PROs at 12 and 24 weeks after baseline respectively.

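### Tables 10.1 and 10.2 regress each patient-reported outcome on DAS28 alone; DAS28 contains a patient health rating, and no planned analysis shows how much of the association comes from it

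*SAP*

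**What the plan says.** The SAP takes DAS28 as its measure of disease severity. Its rule for Table 10.1 is: "Associations between disease severity (measured by DAS28) and PROs (HAQ DI score, SF-36 domain scales, EQ-5D-3L index, WPAI outcomes) will be analyzed", with one single-predictor linear model for every outcome. Changes are handled in the same way: "separate bivariate liner regression models will be estimated to identify the association between change in DAS28 and change in each of the PROs". This is Table 10.2, which covers weeks 12 and 24. No covariates are named for either table, and no version of DAS28 other than the full score is used.

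SAP 3.5.2 builds DAS28 from tender joints, swollen joints, ESR or CRP, and a rating by the patient: "Ask the patient to make a 'global assessment of health' which will be indicated by marking a 10 cm line". Protocol 9.2.4.7 has the same four components. Both documents give the rating a weight of 0.014. The protocol formulas say it is entered in cm; the SAP formula gives no unit.

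The protocol's schedule (Table 1) places DAS28 and the HAQ DI, SF-36, EQ-5D and WPAI at the same visits. SAP 2.3 lists both association analyses as exploratory objectives.

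**The concern.** The patient supplies the outcome and also one component of the predictor. Someone who feels generally unwell may mark the global line worse and also answer the questionnaires worse, whatever the joints and blood marker show. The closest neighbours are the SF-36 general health items: item 1 asks for an overall rating of one's health, and one statement in item 11 does much the same.

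The tables are titled as associations with disease severity. A reader will probably take a clear slope as evidence that joint and inflammatory activity tracks function, quality of life and work. If a material part of the slope comes from the shared rater, that reading is too strong, and the planned output gives no means of telling.

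**Working it through.** The documents give no expected slope, correlation or power for Tables 10.1 and 10.2, so there is no planned figure to reproduce. The check is how much correlation the patient rating could contribute.

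**Inputs from the documents**
- Weight of the rating: 0.014 (SAP 3.5.2, protocol 9.2.4.7).
- Line length: 10 cm (both).
- Two-sided 5% tests (protocol 9.7.3).
- About 100 patients: 90 after the protocol's 10% drop-out, 87 after the SAP's 13%.

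**Inputs assumed, not in the documents**
- Tender joints: mean 8, SD 5. Swollen joints: mean 6, SD 4. Median ESR 30, SD of ln(ESR) 0.7.
- Global rating: mean 50, SD 22 on 0-100 (SD 2.2 in cm).
- Correlation of rating with outcome: 0.3, 0.5 or 0.7. Outcome unrelated to joints and ESR.

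**Step 1: largest possible contribution to the score.** In cm: 0.014 × 10 = 0.14 DAS28 points. On 0-100: 0.014 × 100 = 1.4 points.

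**Step 2: correlation from the rating alone.** If nothing else in DAS28 relates to the outcome,

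r = r(rating, outcome) × 0.014 × SD(rating) / SD(DAS28).

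The assumed inputs give SD(DAS28) of about 0.80 on 0-100 and about 0.75 in cm.

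| Rating-outcome correlation | Scored 0-100: r × 0.014 × 22 / 0.80 | Entered in cm: r × 0.014 × 2.2 / 0.75 |
|---|---|---|
| 0.3 | 0.12 | 0.01 |
| 0.5 | 0.19 | 0.02 |
| 0.7 | 0.27 | 0.03 |

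Simulating 4,000 studies of 90 patients gives mean correlations of 0.11, 0.19 and 0.26 on 0-100, and 0.01 to 0.03 in cm, in line with the formula. The two-sided 5% critical value is t/√(t² + n − 2) = 1.987/√(1.987² + 88) = 0.207 at n=90 (0.211 at n=87). The slope is significant in about 17-20%, 42-43% and 70-72% of simulated studies on 0-100, across repeated runs. It is significant in about 5% in cm, and in about 5% when the rating is left out.

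**Step 3: sensitivity to the assumed SDs.** With SD(rating) 15 to 25 on 0-100, SD(DAS28) 0.8 to 1.3 and the same correlations, r runs from 0.05 to 0.31. In cm it runs from 0.005 to 0.031. At SD(rating) 22 and SD(DAS28) 1.3, the 0-100 values are 0.07, 0.12 and 0.17, all below 0.207.

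**Step 4: a case where joints and marker do relate to the outcome.** Assume the other components have SD 0.8, correlate 0.3 with the outcome and 0.4 with the rating, and the rating correlates 0.5 with the outcome. Removing the rating then takes r from 0.41 to 0.30 on 0-100, but only from 0.315 to 0.300 in cm.

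These figures concern scores at a visit. The formula in step 2 also applies to Table 10.2 with SDs and correlations of changes, for which the documents give no values.

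**The case against.** The best defence is that the plan asks only for the association between DAS28 and each outcome, calls it exploratory, and answers it with a plain regression on the named score. That stands: an unadjusted regression is an acceptable description, and the full DAS28 models should stay. It is also true that the only unit in either document is cm, under which the effect is negligible. But the SAP formula omits the unit, so the plan does not settle which case applies.

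Four stronger readings are tempting, and the documents do not support them.

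- *That SAP 3.5.3 is contradicted.* It says "Baseline demographics and clinical characteristics will be used in statistical analysis models", but names no table and no covariate set. The Table 11 models and the ANOVA adjusted for baseline severity (SAP 5.3) satisfy it.
- *That the missing covariates cause the overlap.* Leaving out age, sex and comorbidity raises possible confounding, which is a different matter. Adding them would not remove the shared rating.
- *That the association is arithmetically built in.* The global rating is not an item of the HAQ DI, SF-36, EQ-5D-3L index or WPAI. The overlap is one of rater and construct.
- *That rejection rates up to about 72% are false positives.* In those simulations the DAS28-outcome association is truly non-zero, so rejecting is correct for the question the SAP asks. It would mislead only as evidence about joints and inflammation.

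Two limits on the evidence also stand. The same-visit timing rests on the schedule, since the CRF accepts the most recent DAS28 if one was calculated. The readable CRF text shows no field for the global rating, although figures are missing, so its absence is not certain.

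**Conclusion.** The point holds as one of interpretation. DAS28 is the sole predictor, it includes a patient rating scheduled alongside the outcomes, and no planned analysis shows the association without it. The rating alone could contribute a correlation of about 0.11 to 0.26 if scored 0-100, but about 0.01 to 0.03 if entered in cm. Both ranges rest on assumed SDs and correlations, and on an outcome unrelated to the other components. The documents do not establish that the effect is large; they leave its size open because the SAP states no unit. The primary analysis is unaffected, and the change is desirable but not essential.

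**What to change.** 1. Reconcile the DAS28 formulas in protocol 9.2.4.7 and SAP 3.5.2 first. They differ on the stated unit of the global rating and on CRP: the protocol uses 0.36 × ln(CRP) plus 0.96, whereas the SAP uses 0.70 × ln(ESR or CRP) with no constant.
2. In SAP 5.5, keep the DAS28 models and label them unadjusted.
3. Beside each model in Tables 10.1 and 10.2, report the same regression on DAS28 without the patient term: 0.56 × √tender28 + 0.28 × √swollen28 + the reconciled ESR or CRP term. Recompute it from the joint counts and marker on the CRF, and use the change in this quantity for Table 10.2.
4. State that an association will be described as one with joint and inflammatory disease activity only if the estimate without the global term, with its 95% confidence interval, also supports it.

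The baseline, follow-up and early-termination CRFs already collect the joint counts and the marker, so no new data are needed. The cost is SAP wording and one extra column per table. The downside is that some associations may look weaker.

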Approximately 100 patients diagnosed with RA will be recruited. The planned sample size provides at least 95% power for detecting a statistically significant improvement in HAQ-DI (Δ HAQ-DI < 0) assuming a mean Δ HAQ-DI of -0.21 and a standard deviation of 0.5 (reference 11), at two-sided significance level of 0.05 and accounting for a 10% dropout rate. The sample size also provides at least 95% power for detecting a statistically significant clinically meaningful improvement in HAQ-DI (Δ HAQ-DI < -0.22) assuming a mean Δ HAQ-DI of -0.5 and a standard deviation of 0.7, at two-sided significance level of 0.05 and accounting for a 10% dropout rate. For the secondary endpoint WPAI, the sample size provides 63% power for detecting a statistically significant improvement in “hours of work lost” at two-sided significance level of 0.05 and accounting for a 10% dropout rate, assuming a mean change in “hours of work lost” of 10 and standard deviation of 30 and assuming a 55% employment rate in the study population.

9.6 **Data Management and Storage Process**

9.6.1 **Data Management**

Data management and data quality check will be performed to remove errors and inconsistencies in order to assure the appropriateness of the study data set to assess the study objectives. Data entry screens will be developed and tested prior to initiating data collection to reduce data entry errors. If required, IMS will provide AbbVie with data for analysis.

Each site coordinator will be instructed to answer patients’ queries which may arise in relation to the questionnaires and check the patients’ input to make sure all questions are answered.

9.6.2 **Storage Process**

Following data quality checks, each dataset will be converted to SAS and merged for analysis. All information included in the CRF and the patients’ questionnaires will be checked in order to detect possible queries to solve and will be extracted to a specifically designed database, where it will be validated by IMS personnel to ensure its quality. Finally, data analysis will be conducted and final results reported.

The databases will be stored in IMS data servers. Data servers are submitted to daily backups in order to increase the security on all data managed in the collection process.

All paper based questionnaires will be stored in a secured, locked area for a period of seven (7) years, after which all data will be shred using an agency specialized in disposal of confidential documents.

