9.7.3 Planned Methods of Statistical Analysis

All statistical tests will be two-tailed with a significance level of 0.05. Descriptive statistics will be provided. Descriptive analysis will be conducted on all key parameters and presented as mean, standard deviation, minimum, maximum, and median when continuous and as "n" and percent when categorical. Change from adalimumab initiation to 24 weeks will be calculated and evaluated for significant improvements using paired t-tests / ANOVA for parametric and Wilcoxon signed-rank for non-parametric data. Analysis will be also be conducted by severity level (moderate vs severe), disease duration quartile (to compare to prior work) and up to two (2) other subgroups. Cochran-Armitage test of trends or other similar methods may be used to compare categories of subjects.

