9.7.8 Additional Analysis

Additional analysis will explore the potential modifying effects of baseline measures on the changes in primary and secondary efficacy outcomes. These measures will include age, gender, baseline severity, and other diagnoses/co-morbidities. The analysis will specifically test for differential changes across the subgroups defined by the potential modifiers using general linear models.

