4. SAMPLE SIZE AND POWER

Approximately 100 patients diagnosed with RA will be recruited. The sample size was calculated by assuming an alpha of 0.05 and a power of 0.80 in a two-sided test, resulting in 52 subjects required to recognize a statistically significant improvement in HAQ DI (-0.21) (11). Given the importance of other secondary endpoints, an improvement of 9.9 ± 25 hours of work time lost requires 58 subjects, assuming an alpha of 0.05 and a power of 0.80 in a two-sided test (12). However, since it is expected that approximately half the study population may no longer be working due to their age, approximately twice this number (100 patients) will be required to achieve the required number of respondents. We have also assumed a drop-out rate of 13% (assuming between 10%-15%).

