5.2 Analysis Plan for Demographic and Clinical Characteristics

- Descriptive statistics will be presented for patient demographics (Excel Table 1), and clinical characteristics (Excel Table 2) for all patients. The following measures will be assessed as of the patient's baseline:
 - Patient age (mean, SD, minimum, maximum, median; categories: 18-34, 35-44, 45-54, 55-64, 65-74, 75+, missing)
 - Gender (male, female, missing)
 - Marital status (married, unmarried, missing)
 - Medical insurance type (National/Public insurance, Private insurance, Employer benefits, other, no insurance, missing)
 - Disease Activity Score in 28 joints - DAS28 (mean, SD, minimum, maximum, median; categories: Remission, Low Disease Activity, Moderate Disease Activity, High Disease Activity, Missing)
 - Number of patients with each of the comorbidities at baseline visit (See 3.5.2), and number of patients with any of these comorbidities

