- In Excel Table 11, separate multivariate generalized linear models (GLM) will be estimated to test for the differential changes in primary and secondary efficacy outcomes after baseline, across the subgroups defined by the potential modifiers, including age, gender, baseline severity, and other diagnoses/comorbidities.

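### SAP Table 11 tests effect modification across subgroups of age and baseline severity although continuous age and DAS28 are collected; if the relation is roughly linear, this gives up power in about 90 patients

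*SAP*

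**What the plan says.** SAP 5.5 describes Table 11 as a set of separate models testing whether the changes in primary and secondary outcomes differ "across the subgroups defined by the potential modifiers, including age, gender, baseline severity, and other diagnoses/comorbidities". Protocol 9.7.8 plans to "specifically test for differential changes across the subgroups defined by the potential modifiers using general linear models". Neither section gives cut points, a number of groups or the form in which age and severity enter the model. The SAP refers to table shells that are not part of the documents.

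Groups are defined in other places:

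- **Severity.** SAP 3.5.2 has moderate (DAS28 between 3.2 and 5.1) and "Severe (DAS28>5.1". Eligibility requires DAS28 above 3.2, so these are the only two groups for enrolled patients.
- **Age.** SAP 5.2 lists "categories: 18-34, 35-44, 45-54, 55-64, 65-74, 75+, missing", but for the descriptive Table 1.

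Continuous versions exist. The baseline patient questionnaire asks for age in years. The baseline CRF records joint counts, ESR or CRP, and the DAS28 score if calculated. In SAP 5.5 itself, Tables 10.1 and 10.2 regress the outcomes, and their changes, on DAS28 and its change.

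**The concern.** Table 11 exists to find out which baseline measures modify the change in outcomes. A linear model accepts age and DAS28 as they are. Cutting them into groups treats a patient just above 5.1 like one far above it, and a patient just below like one near 3.2. When the true relation is a trend, that discards information, and a real modifier is more likely to be reported as absent. The plan gives no reason for using groups as model terms and handles DAS28 differently in two adjacent tables. Leaving the cut points open also allows them to be chosen after the data are seen.

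**Working it through.** **Inputs from the documents.** Protocol 9.5: "Approximately 100 patients diagnosed with RA will be recruited", with 10% dropout, so about 100 × 0.90 = 90 evaluable. SAP 4 assumes 13%, so 87. Protocol 9.7.3: "All statistical tests will be two-tailed with a significance level of 0.05". Employment is 55% in Protocol 9.5 and about half in SAP 4.

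**Assumed, because the documents are silent.** A linear association with correlation r between the modifier and the change; the share of severe patients; the age distribution.

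**The plan's own figures.** Neither document states power for Table 11. The power statements in Protocol 9.5 do reproduce by the noncentral t for a paired test, so its sample sizes are a sound base:

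- HAQ-DI: 0.21/0.5 = 0.42, n = 90: 97.6% (stated at least 95%).
- HAQ-DI against -0.22: (0.50 - 0.22)/0.7 = 0.40, n = 90: 96.4% (stated at least 95%).
- WPAI hours: 10/30 = 0.333, n = 0.55 × 90 = 49.5: 63.3% (stated 63%).

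**Method for Table 11.** Power comes from the noncentral F with noncentrality λ = n·R²/(1 - R²).

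- Continuous term: R² = r², 1 and n - 2 degrees of freedom.
- Two groups with a share p on one side of the cut: r is multiplied by φ(c)/√(p(1 - p)), where c is the normal quantile of p. This gives 0.798 at 50/50, 0.759 at 70/30 and 0.700 at 80/20.
- Six age bands: R² is multiplied by the between-band share of the variance, about 0.93-0.94 for assumed age means of 50-58 and SDs of 12-14, with 5 degrees of freedom.

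**Result at n = 90, r = 0.286** (chosen so that the continuous test has 80% power):

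| Coding | R² | λ | Power | Loss (points) |
|---|---|---|---|---|
| Continuous | 0.286² = 0.0818 | 8.02 | 80% | - |
| 50/50 split | (0.286 × 0.798)² = 0.0521 | 4.95 | 59.5% | 20.5 |
| 70/30 split | (0.286 × 0.759)² = 0.0471 | 4.45 | 55.0% | 25.0 |
| 80/20 split | (0.286 × 0.700)² = 0.0401 | 3.76 | 48.3% | 31.7 |
| Six age bands (5 df) | 0.0818 × 0.937 = 0.0766 | 7.47 | 50% | 30 |

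A simulation at r = 0.29 (4,000 runs) gave 80.0% continuous, 60.0% for a median split and 51.6% for six bands. At n = 87, with r reset to 0.291 so that the continuous test again has 80% power, the two-group losses are almost the same (20.6 points at 50/50, 25.0 at 70/30).

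**Sensitivity to r, 50/50 split, n = 90.** The loss is 5.6 points at r = 0.12, 9.3 at 0.15, 12.7 at 0.18, 15.8 at 0.20, 15.0 at 0.36 and 8.1 at 0.42. It is largest, about 20 points, near r = 0.26-0.29. A 90/10 split at r = 0.286 loses 44.3 points.

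**WPAI overall work impairment.** Only employed patients count: 0.55 × 90 = 49.5, or 0.50 × 87 = 43.5. The same formula at r = 0.286 gives 54% continuous against 37% at a 50/50 split with 49.5 patients, and 49% against 33% with 43.5.

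**The DAS28 input.** Protocol 9.2.4.7 scores the CRP version with 0.36·ln(CRP) + 0.96. SAP 3.5.2 uses 0.70·ln(ESR or CRP) with no constant. The two agree only where 0.34·ln(CRP) = 0.96, that is at CRP = exp(2.82), about 16.8 mg/L. Elsewhere the same patient gets two different scores.

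**The case against.** The strongest reply is that the coding being criticised is not written down. A reader might infer that Table 11 will use the six age bands and spend five degrees of freedom on age. The documents do not support that: the bands belong to Table 1, nothing links them to Table 11, and the shells are not available. The six-band figure therefore applies only if those bands were used. The wording about subgroups does stand, in both documents, and any grouping of a linear modifier loses power.

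Severity is also collected as a category: the CRF asks for moderate or severe, DAS28 is recorded only if calculated, and Protocol 9.7.3 plans analyses by severity level. Table 11 may mean that recorded status. But DAS28 is needed for eligibility and its components are on the CRF, so a baseline score should usually be available.

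The power comparison uses single-modifier tests, whereas the SAP names multivariate models, and the assumption of linearity favours the continuous term. Both are fair limits on the size. The DAS28 formula conflict is not an argument for grouping, because the cut at 5.1 depends on the same score.

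Finally, the table is exploratory, with no power claim and no decision resting on it. That is correct, and it keeps the point minor.

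**Conclusion.** The point holds as a minor weakness in an exploratory analysis. Both documents plan grouped comparisons for age and severity, continuous values are collected, and no reason for grouping is given. Under a roughly linear relation, grouping loses power at every correlation and split examined. The size is conditional: at n = 90 and an assumed r of about 0.29, power drops from about 80% to about 55-60% with two groups (70/30 to 50/50) and to about 50% with six age bands. The loss is about 6-13 points at a 50/50 split for r of 0.12-0.18, and larger for lopsided splits.

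A reader might take a fixed loss of 15 to 30 points as a property of the plan. It is not, because the correlation, the share of severe patients and the age distribution are all absent from the documents. Nor does the point touch the primary analysis, which uses no subgroups.

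**What to change.** Reconcile the DAS28-CRP formula between Protocol 9.2.4.7 and SAP 3.5.2 first; this is needed for the moderate/severe cut as well as for a continuous term.

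Then amend SAP 5.5 (Table 11):

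- Enter age and baseline DAS28 as continuous terms and base the modification tests on them.
- Report each slope with its 95% confidence interval, for example per 10 years and per 1 DAS28 unit.
- Check linearity with a residual plot or a quadratic term.
- Keep moderate/severe and age-group means as descriptive rows, with their cut points stated in advance. This still shows the subgroups that Protocol 9.7.8 asks for.

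The cost is SAP wording and the matching table shell, plus the formula reconciliation; no new data are needed. The downside is that a linear trend is assumed, so a threshold or U-shaped effect could be missed unless the linearity check is done.
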